## **10.2 Secondary, Exploratory and Exploratory Sub-Study Efficacy Endpoint Analysis**

Secondary efficacy endpoints are summarized in Section 5.2, and involve alternative analyses of DRSS results, showing the proportion of patients who develop sight-threatening complications of DR (DME & PDR). Measures of kidney function (UACR and eGFR) are exploratory efficacy endpoints. Exploratory sub-study endpoints are derived from OCT-Angiography, Ultra-wide field fluorescein angiography, Ultra-wide field color photographs, and electroretinography. Details of these variables and their analysis are contained in separate SAPs.

Normality assumption will be tested for any endpoint of continuous nature. If normality assumption is violated, appropriate transformation and/or non-parametric analysis will be employed. Otherwise, all secondary, exploratory and exploratory sub-study endpoints of continuous nature will be analyzed using ANCOVA model, and all inferential analyses will use a 2-sided 5% significance level. For the exploratory efficacy endpoints UACR and eGFR, for internal decision-making purposes, a 1-sided 10% significance level will be used. Whenever possible, a mixed model repeated measures (MMRM) model will be utilized to analyze this data. The model will include change from baseline as the dependent variable. The p-value and 95% CI from the model is baseline parameter adjusted.

For MMRM, visit will be treated as the repeated variable within a subject. Within-subject error, an unstructured variance-covariance will be applied; in case of non-convergence, compound symmetry will be used. MMRM model for UACR and eGFR is adjusted by the baseline HbA1c, Baseline Systolic BP, log-transformed Baseline UACR, and ACEi/ARB use.

Secondary, exploratory and exploratory sub-study endpoints of a dichotomous nature will be analyzed using the same approach as outlined for the primary efficacy endpoint.

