#### **5.2 Secondary Efficacy Endpoints**

Secondary efficacy endpoints include:

- Proportion of subjects with a worsening in the study eye DRSS of  $\geq 2$  steps at week 48
- Mean change from baseline in DRSS in the study eye at week 48
- Proportion of subjects with an improvement or worsening in the study eye DRSS of  $\geq 3$  steps at week 48.
- Subjects with criterion step improvement in DRSS at week 48 ( $\geq 2$  steps improvement in the study eye for patients with non-qualified fellow eye and  $\geq 3$  steps improvement on the Person scale for patients with qualified fellow eyes)
- Subjects with criterion step improvement in DRSS at week 48 ( $\geq 2$  steps improvement in the study eye for patients with non-qualified fellow eye and  $\geq 3$  steps improvement on the Binocular scale for patients with qualified fellow eyes)
- Proportion of patients developing center-involved Diabetic Macular Edema (DME) or Proliferative Diabetic Retinopathy (PDR) or PDR-related outcomes during treatment period based on Clinical Data. Due to variation in clinician criteria for reporting DME and PDR adverse events, all events will be reviewed and AEs that were not treated and were not validated in FPRC interpretation of imaging data will be censored from the results.
- Proportion of patients developing center-involved DME or PDR or worsening of  $\geq 2$  steps DRSS at week 48 based on Central Image Reading Center Evaluation
- Primary and secondary assessments in qualified fellow eyes and all qualified eyes (study eyes and qualified fellow eyes).

- Primary and secondary endpoints assessed at week 12, 24 and 36.

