## 6 DATA PREPARATION

Except for the laboratory data (clinical laboratory assays, PK and biomarker data) and imaging data, all reported study data will be recorded on the eCRFs supplied by TrialRunners (TR) using iMedNet Electronic Data Capture (RDC). Only the Principal Investigator and authorized study staff according to the Delegation of Responsibilities log are entitled to make entries on the eCRF. Data from source documents will be entered into RDC by site personnel. The laboratory and imaging data will be incorporated into the study database electronically. The details of the laboratory data transfer can be found in the Data Transfer Agreements (DTAs) and TR's Standard Operating Procedure (SOP) on electronic data importation.

All ocular image data (fundus photographs, FA and SD-OCT) will be transmitted to the Eyekor Excelsior data platform. The Wisconsin Fundus Photograph Reading Center (FPRC) will assess all screening images to confirm subject eligibility. The FPRC will also grade all 7-field or 4-field wide color fundus photographs for DRSS, FA data, and SD-OCT data. Details are contained in the FPRC image grading charter. Ultra-wide field fluorescein angiography data will be graded by the Campane Center for Advanced Imaging at the Cole Eye Institute (CCAI) using their custom software. Details are contained in the CCAI UWF-FA charter. Electrotoretinographic data will be evaluated by LKC Technologies using their custom software. The FPRC, CCAI and LKC Technologies will store graded data in Excelsior and this data will be transferred to TR per the DTA and incorporated into the study database electronically. OCT-A and UWF-color photographs will be graded by the Boston Image Reading Center (BIRC) using their custom software. Data will be stored at BIRC and transferred TR per the DTA and incorporated into the study database electronically. Source raw images will be stored at study sites. Image grading source data will be stored at the reading centers.

All analyses outlined in this document will be carried out after the following has occurred:

- All data management requirements are met according to TR standard operating procedures, including data entry, performance of edit and validation checks, documentation and resolution of data queries, and database lock with written authorization provided by appropriate TR and Sponsor personnel;
- Protocol deviations have been identified and status defined (major/minor deviations);

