- Analysis populations have been determined, and

- Randomized treatment codes have been unmasked.

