**SIGNATURES**

The undersigned have approved this Statistical Analysis Plan for use in this study.

[name], Biostatistician, Trial Runners, LLC	Date
[name], Chief Medical Officer, Aerpio Therapeutics, Inc.	Date
[name], Vice-President of Clinical Development, Aerpio Therapeutics, Inc.	Date

Ultra-wide field Color Photographs were obtained in study AKB-9778-CI-5001 as an exploratory sub-study. Images were obtained from both eyes, at pretreatment Baseline, Week 24, and Week 48/EOT visits, using either an Optos 200Tx or Optos California system. Data acquisition and transmission protocols were specified in a study manual. All images were uploaded to the Eyekor Excelsior platform. Images were graded by the Boston Image Reading Center using their custom software. Grading will follow ETDRS DRSS criteria, but the analysis area will include the entire ultra-wide field rather than be limited to the central 7-fields. DRSS grades ranging from 10-85 will be converted to an ordinal score ranging from 1-11. Monocular scores will be converted to Person and Binocular scores in subjects with qualified fellow eyes as is specified for the primary DRSS outcome.

The primary endpoint of this substudy is the percentage of subjects with an improvement in study eye severity of DR (ETDRS DR Severity Score or DRSS) of  $\geq 2$  steps at 48 weeks without need for treatment of PDR or DME (by IVT, laser, or vitrectomy) in the study eye.

The primary hypotheses will be tested in the MITT population using a Fisher's Exact Test with a 2-sided 5% significance level. AKB-9778 15mg twice daily will be tested first. If this is found to be statistically significant, then AKB- 9778 15mg once daily will be tested for statistical significance, at the same significance level. Cochran-Mantel-Haenszel (CMH) test stratified for baseline ETDRS DRSS (levels 4, 5 and 6) will also be used for testing primary hypothesis in the MITT population. Missing data will be imputed using Last Observation Carried Forward (LOCF); baseline values will not be carried forward. For rescued eyes the last observation pre-rescue will be carried forward.

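### SAP 10.2 makes ANCOVA depend on an unspecified normality test run after unmasking, leaving the method for mean DRSS change unfixed

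*SAP*

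**What the plan says.** SAP 10.2, on secondary, exploratory and sub-study endpoints, sets the rule in three sentences. The first lays down the check: "Normality assumption will be tested for any endpoint of continuous nature". The second covers failure of that check and leaves the replacement method open: "If normality assumption is violated, appropriate transformation and/or non-parametric analysis will be employed". Only the third, for the case where the check is passed, names a model: "Otherwise, all secondary, exploratory and exploratory sub-study endpoints of continuous nature will be analyzed using ANCOVA model".

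A separate sentence adds: "Whenever possible, a mixed model repeated measures (MMRM) model will be utilized to analyze this data". Its rank relative to the normality test is not stated. The section then refers to a baseline-adjusted p-value and 95% CI from the model.

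On timing, SAP section 6 says "All analyses outlined in this document will be carried out after the following has occurred" and ends its list with "Randomized treatment codes have been unmasked".

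Protocol 11.7 assigns continuous secondary and exploratory variables to ANCOVA and/or mixed models for repeated measures, with no distributional condition. SAP 1.1 (Change from Protocol) is marked not applicable.

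The endpoint most affected is in SAP 5.2: "Mean change from baseline in DRSS in the study eye at week 48". DRSS is a step scale. SAP 3.2 stratifies on levels 4, 5 and 6, and the ultra-wide field photography SAP states "DRSS grades ranging from 10-85 will be converted to an ordinal score ranging from 1-11".

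**The concern.** A preliminary normality test makes the analysis method depend on the observed data. Here both the test and the fallback are undefined, and the choice falls after the treatment codes are open. For a score in whole steps the test is likely to fail because of discreteness alone, even where ANCOVA would perform well. The route left to the analyst is then the one the plan does not describe.

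What is at stake is which result is reported for mean DRSS change. A rank test does not estimate a mean difference, and a transformed analysis estimates it on another scale. The adjusted difference and interval that SAP 10.2 describes could be lost for an endpoint defined as a mean.

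**Working it through.** **1. The plan's own figure.** SAP 3.1 gives more than 85% power with 45 evaluable per arm, 30% versus 5%, Fisher's exact test, two-sided 0.05. Exact enumeration gives 86.3%, and 45 / (1 − 0.10) = 50 per arm. The figure reproduces. It concerns the binary primary endpoint and is not in dispute.

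**2. A spread for DRSS change.** The documents give no SD. One can be derived from the design rates by assuming a normal latent change rounded to whole steps, with negative values meaning improvement. An improvement of 2 or more steps then means a latent change below −1.5.

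- Placebo, mean 0, 5% improving: SD = 1.5 / 1.645 = 0.91.
- Active, 30% improving: mean = −1.5 + 0.524 × 0.912 = −1.02.

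**3. How often the test fails.** Three arms of 50, baseline levels 4, 5 and 6, integer change, 5% level. Shapiro-Wilk and the 5% level are assumptions. The no-effect rows were run at several SDs because the true SD is unknown.

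| Case | Raw pooled change | ANCOVA residuals, Shapiro-Wilk | ANCOVA residuals, Anderson-Darling |
|---|---|---|---|
| SD 0.8, no effect | 100% | 98% | 100% |
| SD 0.91, no effect | 100% | 95% | 98% |
| SD 0.91, half-step shift | 100% | about 68% | 83% |
| SD 0.91, full design effect | 100% | 94% | 98% |
| SD 1.2, no effect | 100% | 68% | 82% |
| SD 1.5, no effect | 100% | 38% | 58% |
| SD 2.0, no effect | 100% | 16% | 28% |
| SD 2.5, no effect | 85% | 9% | 17% |

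At SD 1.5 the Shapiro-Wilk residual rate runs from about 30% to 41% across shifts and repeat runs. As a control, a truly continuous normal variable is rejected about 5% of the time, so the failures above come from the whole-step scale.

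**4. What it does to error rates.** One active arm versus placebo, 50 per arm, SD 0.91:

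- ANCOVA fixed in advance: type I error 4.8%.
- Best of ANCOVA, Wilcoxon, rank ANCOVA and stratified Wilcoxon: 6.1%.
- A fixed version of the gated rule (ANCOVA if residuals pass, Wilcoxon if not): about 4% to 5% at SD 0.91, 1.2 and 1.5.
- Power at a half-step shift: 74% for ANCOVA, 72–73% for the rank methods.

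ANCOVA holds its level on these discrete data, and the rank methods gain no power over it.

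**5. Which endpoints are exposed.**

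- UACR: the log transform is fixed in SAP 5.3.
- OCT-A, ERG and UWF-FA: their own SAPs name ANCOVA/MMRM with no normality condition, while SAP 10.2 includes sub-study endpoints in its rule. The texts need reconciling.
- eGFR: SAP 10.2 lists MMRM covariates, but no transformation or alternative is fixed.
- Mean DRSS change: nothing is fixed beyond the conditional ANCOVA and the unranked MMRM sentence.

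**The case against.** The strongest reply is that the practical harm is small. That stands: the primary endpoint is binary (Fisher, CMH), secondary endpoints carry no multiplicity control in this Phase 2 trial, and a mechanical version of the gated rule keeps type I error near 5%. SAP 7.2 also requires descriptive means and SDs, so observed mean change is reported either way. Only the inferential difference and its interval are at risk, and a transformation may be used rather than a rank test.

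A reader might infer more than the documents support:

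- That every continuous endpoint is left open. UACR and the three sub-study SAPs are counter-examples.
- That DRSS change cannot pass. This is close to true only if raw change is tested. ANCOVA assumes normal residuals, and those pass in most trials at SD 1.5 under Shapiro-Wilk. The SAP does not say which is tested.
- That MMRM is also displaced. The conditional wording attaches to ANCOVA, and the MMRM sentence stands apart. The text is ambiguous.
- That the method will be picked by looking at treatment effects. Section 6 is a general timing rule for all analyses and does not say this.

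It can also be argued that a test which nearly always fails amounts to a fixed switch, not a data-driven choice. That is fair for raw change, but the switch leads to a method nobody has named.

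**Conclusion.** The point holds for mean change in study-eye DRSS and, less sharply, for eGFR. SAP 10.2 adds a condition that Protocol 11.7 does not have, does not declare it in 1.1, and leaves both the test and the fallback undefined at a stage when the codes are open. Mean DRSS change would probably leave ANCOVA: almost certainly if raw change is tested, and with a probability that depends strongly on spread and effect if residuals are tested.

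These rates rest on rounded-normal change, an assumed test and level, and an SD that the documents do not give. The inflation of type I error is modest. The substantive defect is that neither the method nor the reported estimate for this endpoint is fixed before unmasking. It should be corrected, but it does not threaten the primary analysis or the sample size.

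**What to change.** Before unmasking, amend SAP 10.2 to:

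1. Delete the normality test as a condition for the analysis method.
2. Name one primary model for mean DRSS change at week 48, whatever its distribution. One choice is ANCOVA adjusted for baseline DRSS in the MITT population under the LOCF rule that SAP section 10 sets for secondary endpoints, with MMRM on observed data as supportive. Writing ANCOVA/MMRM without choosing would leave the same gap. For the MMRM, say how pre-rescue values enter, since SAP 7.1 carries them forward even in observed-case analyses.
3. Keep the UACR log transform in 5.3, and name the eGFR model without a distributional condition.
4. State that the sub-study SAPs govern their own endpoints.
5. Name one rank-based sensitivity analysis in advance, for example a van Elteren test stratified by DRSS level. Another named rank method would serve equally well.

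This removes the departure from Protocol 11.7. It costs SAP wording and one extra table. In the simulation, fixing ANCOVA lost no power against the rank methods.

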8.3.2 Randomization and Allocation to Treatment Group

Approximately 150 subjects will be treated in the study.

Using a central IWRS randomization system, eligible subjects will be assigned in a double-masked fashion 1:1:1 to one of the 3 treatment groups. To maintain balance between treatment groups with respect to DR severity, randomization will be stratified by Screening ETDRS DRSS (levels 43, 47 and 53). The number of study eyes randomized with Screening ETDRS DRSS level 43 will be capped at 50.

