11 DATA ANALYSIS

11.1 Sample Size Determination

Estimates for sample size calculations are derived from published data from the analysis of the effect of ranibizumab (Lucentis) and aflibercept (Eylea) intravitreal administration regimens on DR severity score in the RISE/ RIDE studies and VIVID/VISTA studies, respectively, in which at least 28-46% of subjects improved by ≥ 2 steps after 12 months of treatment.

With 45 evaluable subjects per treatment group, the study has $>85\%$ power (based on Fisher’s Exact Test and a 2-sided alpha =0.05) to demonstrate a statistically significant improvement in percent of subjects improving by ≥ 2 steps on the ETDRS severity scale, assuming underlying rates for active and placebo of 30% and 5%, respectively. Assuming 10% drop-out/non-evaluable rate, a sample size of 50 subjects per treatment arm (approximately 150 total) has been selected.

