### **3.1 Sample Size Considerations**

Estimates for sample size calculations are derived from published data from the analysis of the effect of ranibizumab (Lucentis®) and aflibercept (Eylea®) intravitreal administration regimens on DR severity score in the RISE/RIDE studies and VIVID/VISTA studies, respectively, in which at least 28-46% of subjects improved by  $\geq 2$  steps after 12 months of treatment.

With 45 evaluable subjects per treatment group, the study has  $>85\%$  power (based on Fisher's Exact Test and a 2-sided alpha =0.05) to demonstrate a statistically significant improvement in percent of subjects improving by  $\geq 2$  steps on the ETDRS diabetic retinopathy severity scale, assuming underlying rates for active and placebo of 30% and 5%, respectively. Assuming 10% drop-out/nonevaluable rate, a sample size of 50 subjects per treatment arm (approximately 150 total) was selected.

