**SIGNATURES**

The undersigned have approved this Statistical Analysis Plan for use in this study.

[name], Biostatistician, Trial Runners, LLC	Date
[name], Chief Medical Officer, Aerpio Therapeutics, Inc.	Date
[name], Vice-President of Clinical Development, Aerpio Therapeutics, Inc.	Date

OCT-Angiography (OCT-A) images were obtained in study AKB-9778-CI-5001 as an exploratory sub-study. Images (3mm x 3mm and 6mm x 6mm images, centered on the fovea) from study and fellow eyes were obtained at pretreatment Baseline, Week 12, Week 24, Week 36 and Week 48/EOT visits. Data acquisition and transmission protocols were specified in study manuals for Optovue, Zeiss, and Topcon systems. All images were uploaded to the Eyekor Excelsior platform. Images were graded by the Boston Image Reading Center (BIRC) using their custom software. Parameters graded are shown in Table 1. Outcome variables of primary interest are FAZ area, % vessel density, % vessel skeleton density, total vessel length, and non-perfusion area.

Continuous sub-study endpoints of interest will be analyzed using an ANCOVA model, and all inferential analyses will use a 2-sided 5% significance level. Whenever possible, a mixed model repeated measures (MMRM) model will be utilized to analyze this data. The model will include change from baseline as the dependent variable. The p-value and 95% CI from the model is baseline parameter adjusted. For MMRM, visit will be treated as the repeated variable within a subject. Within-subject error, an unstructured variance-covariance will be applied; in case of non-convergence, compound symmetry will be used.

Categorical variables will be tested using a Fisher's Exact Test with a 2-sided 5% significance level. AKB-9778 15mg twice daily will be tested first. If this is found to be statistically significant, then AKB- 9778 15mg once daily will be tested for statistical significance, at the same significance level. Cochran-Mantel-Haenszel (CMH) test stratified for baseline values will also be used for testing. Missing data will be imputed using Last Observation Carried Forward (LOCF); baseline values will not be carried forward.

The relation between change in DRSS from baseline to Week 48/EOT visit and baseline FAZ Area, baseline Vessel Skeleton Density (6x6), baseline Total Vessel Length (6x6), and baseline Non-perfusion Area (6x6) will also be calculated.

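### The ANCOVA/MMRM models for the non-DRSS exploratory endpoints omit the DRSS stratum used to randomise: a minor loss of precision if the stratum is prognostic, and cheap to repair

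*SAP*

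**What the plan says.** Protocol 8.3.2 sets the randomisation: "To maintain balance between treatment groups with respect to DR severity, randomization will be stratified by Screening ETDRS DRSS", with levels 43, 47 and 53. SAP 3.2 repeats the stratification and writes the levels as 4, 5 and 6.

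SAP 10.2 covers the continuous secondary, exploratory and sub-study endpoints. They are analysed by ANCOVA, or by MMRM where possible, on change from baseline, and "The p-value and 95% CI from the model is baseline parameter adjusted". For the renal endpoints it goes further: "MMRM model for UACR and eGFR is adjusted by the baseline HbA1c, Baseline Systolic BP, log-transformed Baseline UACR, and ACEi/ARB use". The separate OCT-A, ERG and UWF-FA plans carry the same baseline-parameter sentence. None of them names the DRSS stratum.

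Elsewhere the SAP does use DRSS. SAP 10.1 adds a CMH test stratified by baseline DRSS to Fisher's exact test for the primary endpoint, and SAP 10.2 extends that approach to dichotomous endpoints.

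On OCT-A equipment, the sub-study plan says: "Data acquisition and transmission protocols were specified in study manuals for Optovue, Zeiss, and Topcon systems". It specifies no vendor term.

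**The concern.** A factor used to stratify randomisation would normally appear in the analysis model. Stratifying removes between-arm variation due to that factor. A model without the factor still counts that variation as residual error, so if the factor predicts outcome, the standard error is overstated and the test is conservative.

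The stratum could plausibly be prognostic here. The ERG plan describes the LKC composite score as a measure of vision-threatening retinopathy, and all three of these sub-study plans intend to relate their baseline measures to DRSS change.

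What is at stake is precision on exploratory endpoints. That has some practical use, since SAP 10.2 reads UACR and eGFR at a one-sided 10% level for internal decisions. In the sub-studies the term also has a second use. They run at a subset of sites, and no stratification by sub-study is described, so DRSS balance between arms is not assured within them.

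**Working it through.** **The plan's own figure.** The sample-size inputs (SAP 3.1, Protocol 11.1) are "With 45 evaluable subjects per treatment group", "assuming underlying rates for active and placebo of 30% and 5%, respectively", Fisher's exact test and "2-sided alpha =0.05". Summing the exact binomial probabilities of all tables with Fisher p ≤ 0.05 gives power of 86.3%, which agrees with the stated figure of more than 85%. Allowing for dropout, 45/(1 − 0.10) = 50 per arm. Neither figure depends on the continuous models.

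**Omitting the stratum.** Let R² be the share of the residual sum of squares that the stratum term removes in the fitted data. For a term balanced across arms, the ratio of standard errors, and so closely of interval widths, is

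ratio (omitted/included) = √[ 1/(1 − R²) × df with term / df without term ]

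At N = 3 × 45 = 135, three arm means and one baseline slope leave 131 df. Two stratum terms leave 129. At N = 45, an illustrative sub-study size, the figures are 41 and 39. So √(129/131) = 0.992 and √(39/41) = 0.975 are multiplied by 1/√(1 − R²):

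| R² (assumed) | Large sample | N=135 | N=45 |
|---|---|---|---|
| 0.01 | 1.005 | 0.997 | 0.980 |
| 0.02 | 1.010 | 1.002 | 0.985 |
| 0.05 | 1.026 | 1.018 | 1.001 |
| 0.10 | 1.054 | 1.046 | 1.028 |
| 0.20 | 1.118 | 1.110 | 1.090 |

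Break-even is at R² = 1 − df with/df without: 2/131 = 0.015 and 2/41 = 0.049. These are also the shares that an irrelevant two-df factor would remove on average by chance. If R² is read instead as the population share, the large-sample column applies, and the cost appears only through the t quantile and any stratum-by-arm imbalance. The extra renal covariates reduce the df slightly and barely move these results.

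**Change in DRSS.** Before dosing, fundus photographs are scheduled only at screening (Protocol Appendix A), so baseline DRSS comes from the visit that supplies the stratum. In a simulation with 45 per arm, SD 1.2 and slope −0.3 per level (assumed), the standard error was 0.2572 unadjusted, 0.2519 with baseline DRSS and 0.2518 with stratum indicators. Adding the stratum gains nothing.

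**OCT-A vendor, interval width.** A simulated ANCOVA on change used two arms, a baseline–follow-up correlation of 0.7, and additive offsets between adjacent vendors of 0 to 4 true between-subject SDs. The width ratio (vendor omitted/included) was 0.926–1.002 at 10 per arm, 0.970–1.042 at 20 and 0.988–1.062 at 45. At the smallest size, leaving vendor out usually gives the narrower interval.

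**OCT-A vendor, imbalance.** Set the within-vendor baseline SD to 1, the correlation to ρ = 0.7, the vendor offsets to −δ, 0, +δ, and the drug effect to nil. Suppose the vendor mix is 50/30/20 in one arm and 20/30/50 in the other (assumed, and a marked imbalance). The arms' mean offsets differ by D = 0.6δ, and the within-arm offset variance is V = 0.70δ² − 0.09δ² = 0.61δ². The raw change difference is zero, but the shared baseline slope is diluted to −(1 − ρ)/(1 + V). The adjusted difference is therefore (1 − ρ)D/(1 + V):

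- δ = 1: 0.3 × 0.6/1.61 = 0.11 SD
- δ = 2: 0.3 × 1.2/3.44 = 0.10 SD

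A vendor factor brings this to zero.

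**The case against.** The strongest reply is that no loss has been shown. The documents give no partial R², no SD and no sub-study size. The relevant R² is only what DRSS adds after the endpoint's own baseline, and for renal endpoints after four named covariates, across the narrow range of levels 43 to 53. In a small sub-study that could fall below break-even. This stands, and it is why the effect is given as a range under assumptions. It does not remove the case for adding the term: if the stratum carries no information the cost is slight, and if it does the gain is larger.

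A reader might infer that all the continuous models ignore the stratification factor. They do not, because mean change in DRSS is adjusted for baseline DRSS. The final adjudicated grade could differ from the screening grade used in IWRS, and a linear term is not the same as indicators, but little is left to gain.

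A reader might also infer that pooling three vendors' OCT-A systems makes those intervals wider than the design allows. The documents do not support that. Vendor was not a randomisation factor, so the design promises no precision from it. Protocol 9.2.1 has OCT-A taken on an SD OCT machine and, under SD OCT, requires one instrument type per subject, so an additive vendor offset cancels in the raw change. Only the possible distortion from a chance vendor-by-arm imbalance remains. It averages out over randomisations, and nothing in the documents shows that it occurred. Vendor differences in scale were not sized here.

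**Conclusion.** The omission is real for UACR, eGFR, ERG, OCT-A and UWF-FA, and its consequence is small. If the stratum has an R² of 0.05 to 0.20, intervals are about 2% to 11% too wide at N=135 and 0% to 9% too wide at N=45. Below the break-even values there is no gain or a slight loss. These figures assume strata balanced across arms and a single-visit ANCOVA as a stand-in for the MMRM. Where the stratum is prognostic, the error is in the conservative direction.

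For OCT-A vendor, the evidence supports a sensitivity analysis and no more. Severity is minor: the affected endpoints are exploratory, and the primary Fisher and CMH tests, the testing order and the sample size do not change.

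**What to change.** In SAP 10.2 and in the OCT-A, ERG and UWF-FA plans, add the IWRS screening DRSS stratum (43/47/53) as a three-level factor to the ANCOVA and MMRM models for UACR, eGFR and the sub-study endpoints. The model for change in DRSS can stay as it is. The cost is SAP wording and 2 degrees of freedom, which matters only in a very small sub-study.

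For OCT-A, tabulate vendor by arm. If numbers per vendor permit, add a sensitivity analysis with vendor as a factor and a common baseline slope. Vendor-specific slopes should not be added: with three vendors they would take the cost from 2 to 4 degrees of freedom, on top of the stratum's 2. The OCT-A parameter table lists no vendor field, so the plan should say where that variable will come from.

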### 5.3 Exploratory Efficacy Endpoints

Change from baseline in urine-albumin-to-creatinine ratio (UACR) and estimated glomerular (eGFR) at week 12, 24, 36 and 48 in the overall MITT population and in the subgroup of subjects with renal insufficiency at baseline (UACR >30 µg/mg for UACR analysis; eGFR <90 mL/min/1.73m^2 for the eGFR analysis) is the exploratory efficacy endpoint used to investigate renal function.

For urine albumin values below the lower limit of quantitation, UACRs will be calculated using the 0.5xLLQ value. Due to the positive skewness, UACR data will be log transformed prior to analysis. The primary outcome will be percent change in geometric mean.

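### The only fallback for a non-converging MMRM is compound symmetry, which understates the Week 48 standard error if the fallback is used and the spread of change grows over visits

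*SAP*

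**What the plan says.** SAP section 10.2 makes ANCOVA the base analysis for continuous secondary, exploratory and sub-study endpoints, then prefers a repeated-measures model: "Whenever possible, a mixed model repeated measures (MMRM) model will be utilized to analyze this data". On the outcome: "The model will include change from baseline as the dependent variable". On the covariance: "Within-subject error, an unstructured variance-covariance will be applied; in case of non-convergence, compound symmetry will be used". Inference is taken from the fitted model: "The p-value and 95% CI from the model is baseline parameter adjusted". No heterogeneous structure, Toeplitz, AR(1) or empirical (sandwich) standard error is named.

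The OCT-A, ERG and UWF-FA sub-study SAPs carry the same covariance rule, with the same fallback: "in case of non-convergence, compound symmetry will be used". The UWF colour-photograph SAP plans no MMRM.

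The main time point is the last visit, for example "Mean change from baseline in DRSS in the study eye at week 48" (SAP 5.2). Earlier visits also enter: "Primary and secondary endpoints assessed at week 12, 24 and 36". UWF-FA has only Weeks 24 and 48 after baseline. SAP 5.3 lists UACR and eGFR "at week 12, 24, 36 and 48 in the overall MITT population", and section 10.2 gives these two endpoints a one-sided 10% rule for internal decisions. All other inference is two-sided at 5%.

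**The concern.** Read without qualification, compound symmetry means a single variance for all visits and a single correlation for all pairs. The Week 48 treatment contrast is then given a standard error based on the average of the visit variances. If change from baseline is more variable at Week 48 than at earlier visits, that average is too low for the visit that matters most: the confidence interval is too narrow and the test rejects too often. Because no sandwich standard error is planned, nothing in the analysis would correct this.

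At stake are the secondary mean change in DRSS, the exploratory UACR and eGFR comparisons, and the OCT-A, ERG and UWF-FA endpoints.

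**Working it through.** **The plan's own figures.** The documents give no standard error for any MMRM and no SD of change by visit. The only related design figure is the power of the primary test, above 85% with 45 evaluable subjects per arm and rates of 30% and 5%. Exact enumeration of the two-sided Fisher test gives 86.3%, so that figure reproduces, but it does not bear on this point.

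**Inputs.**
- From the SAP: post-baseline visits at Weeks 12, 24, 36 and 48; two-sided 5% level; one-sided 10% for UACR and eGFR; 45 evaluable per arm; 10% dropout.
- Assumed: the SD of change rises linearly from Week 12 to Week 48, by a factor of 1.25, 1.5 or 2.

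**Formula.** With complete, balanced data and a mean for each arm at each visit, the Week 48 contrast is the difference in Week 48 means, with true variance 2σ₄₈²/n. REML under compound symmetry replaces σ₄₈² by the mean of the visit variances. Hence

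R = SE(compound symmetry) / SE(true) = √(mean of σ_t² / σ₄₈²)

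Two-sided error = 2·P(Z > 1.96·R); one-sided 10% error = P(Z > 1.2816·R).

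**Four visits** (Week 12 SD set to 1):

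| SD growth | Visit variances | Mean | R | SE too small by | Two-sided 5% becomes |
|---|---|---|---|---|---|
| 1.25 | 1, 1.174, 1.361, 1.563 | 1.274 | 0.903 | 10% | 7.7% |
| 1.5 | 1, 1.361, 1.778, 2.25 | 1.597 | 0.843 | 16% | 9.9% |
| 2 | 1, 1.778, 2.778, 4 | 2.389 | 0.773 | 23% | 13.0% |

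For the middle row: R = √(1.597/2.25) = 0.843, 1.96 × 0.843 = 1.65, and 2·P(Z > 1.65) = 9.9%.

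**Three visits** (Weeks 24, 36 and 48, as the protocol schedules UACR), same growth lines with Week 12 removed:

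| SD growth, Week 12 to 48 | Mean variance | R | SE too small by | One-sided 10% becomes |
|---|---|---|---|---|
| 1.25 | 1.366 | 0.935 | 7% | 11.5% |
| 1.5 | 1.796 | 0.894 | 11% | 12.6% |
| 2 | 2.852 | 0.844 | 16% | 14.0% |

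**Two visits** (UWF-FA), with the SD 1.5 times larger at Week 48 than at Week 24: R = √(1.625/2.25) = 0.85, and two-sided error is 9.6%.

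**Other directions.** Constant spread with complete data gives R = 1.00. Spread falling from 1.5 to 1 over four visits gives R = 1.26 and two-sided error of 1.3%, so the test is then conservative.

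**Simulation.** In 100,000 trials per scenario (three arms of 45, four visits, AR correlation 0.7), compound symmetry gave two-sided errors of 9.7% and 12.8% for 1.5- and 2-fold growth. Using the Week 48 variance itself gave 4.96% to 5.05% in every growing-spread scenario.

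**Dropout.** Large-sample fits with 10% to 30% missing at the last visit, and correlations from 0.5 to 0.95, gave R between 0.74 and 0.985 in every growing-spread case. With constant spread R was 0.977 to 1.00. Dropout did not reverse the direction in any case tried.

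**The case against.** The strongest reply is that the fallback will rarely be reached. An unstructured matrix for four visits has 4 × 5 / 2 = 10 parameters, against about 150 subjects. SAP section 10 plans LOCF for all secondary efficacy endpoints, so those data are close to complete. With complete balanced data the unstructured REML fit is essentially the pooled sample covariance, and failure is not expected. This stands for the full trial. It is weaker for the sub-studies, which run at a subset of sites and whose size is not stated.

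Second, nothing in the documents shows that the spread grows. This also stands: both the direction and the size of the error are assumptions. UACR is moreover log-transformed for skewness, and its scheduled visits call for the smaller three-visit figures.

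Third, unstructured followed by compound symmetry is at least pre-specified and unambiguous. That is true, but the rule drops the Week 48 variance exactly when the preferred model has failed, and structures that keep it are just as easy to name in advance.

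A reader might also infer that the fallback is likely because SAP 5.3 analyses UACR and eGFR at Week 12, when the protocol does not schedule them. The documents do not support this. A visit with no records adds no row to the matrix; it leaves a 3 × 3 matrix with 6 parameters, which is easier to fit. The note to SAP Table 2 already removes the Week 12 urinalysis window, and baseline values are not carried forward, so LOCF cannot fill Week 12 from baseline. For eGFR, creatinine is part of the monthly chemistry panel (protocol 9.2.2), so Week 12 values could exist in full. The mismatch is a separate matter to reconcile.

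**Conclusion.** The point holds as a conditional weakness. Two things must both happen: the unstructured fit fails, and the spread of change increases towards Week 48. The Week 48 standard error is then 10% to 23% too small with four visits, and two-sided error is 7.7% to 13.0%, for assumed linear SD growth of 1.25- to 2-fold. For three visits the shortfall is about 7% to 16%, and the one-sided 10% rule runs at about 11.5% to 14.0%. These figures assume complete data, model-based standard errors, and the homogeneous form of compound symmetry, which is the plain reading of the term.

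A reader might infer that the trial's Week 48 intervals are generally too narrow. The documents do not support that: they give no SD by visit, and constant or shrinking spread yields no error or a conservative one. Nor is the primary result at risk, since SAP 10.1 tests it with Fisher's exact test and CMH. What remains is secondary and exploratory inference without multiplicity adjustment, most plausibly in the small sub-studies. This is a worthwhile, low-cost improvement and not a serious defect.

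**What to change.** In SAP 10.2 and in the OCT-A and ERG SAPs, replace the compound-symmetry fallback with an ordered list that keeps visit-specific variances: heterogeneous Toeplitz, then heterogeneous AR(1), then heterogeneous compound symmetry. If none converges, use the Week 48 ANCOVA already planned, which takes its residual variance from Week 48 alone.

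For UWF-FA go straight from unstructured to the ANCOVA. With two visits, heterogeneous compound symmetry has two variances and one correlation, which is the unstructured matrix again.

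Allow sandwich standard errors only with a small-sample correction. Uncorrected, they are themselves too small by a factor √((n−1)/n) with visit-by-arm means. At an assumed 10 per arm, two-sided error is 7.9% with a normal reference and 6.2% with a t reference; at 5 per arm it is 11.8% and 7.3%.

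Separately, reconcile the Week 12 UACR and eGFR analyses (SAP 3 and 5.3) with the collection schedule (protocol 6.1, 9.2.2 and Appendix A) and with the note to SAP Table 2.

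The cost is about one sentence in each SAP, slightly more programming and a few more variance parameters. No change to data collection or sample size is needed.
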